## **11.2. Laboratory variables**

In case of derived items in the database (e.g., after transformation to standard units, see DMP), only the derived items will be analysed. Results of all individual laboratory tests will be listed in original and standard units in appendix 16.2 to the clinical trial report.

The following laboratory parameters will be analysed (as available from local laboratories):

Coagulation profile	Point-of-care INR, PT, aPTT, INR, fibrinogen activity via Clauss assay, ROTEM EXTEM CT, ROTEM EXTEM MCF, ROTEM FIBTEM MCF, PlateletWorks platelet count and function
Haematology	Standard panel as per local laboratory
Clinical chemistry	Standard panel as per local laboratory
Safety laboratory analyses	Troponin, ALT/ALP, bilirubin, creatinine

All laboratory values will be classified as normal or abnormal according to the laboratories' reference ranges and indicated as clinically significant or not clinically significant by the investigator on specified ranges. The following approaches will be taken for each laboratory parameter for the statistical analysis:

Quantitative data will be examined for trends using descriptive analysis (number of patients, number of missing values, mean, SD, median, quartiles, minimum, maximum) of actual values at each scheduled time point and changes from baseline to each scheduled time point. In addition, mean concentration vs. time profiles (including standard deviations) will be plotted by treatment to illustrate any time trends.

Qualitative data based on reference ranges will be described according to the categories (i.e., low, normal, high).

Shift tables will be generated illustrating changes with respect to the laboratories' reference ranges between baseline and a defined scheduled time point.

Patient listings will be provided showing individual laboratory abnormalities.

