- Measure haemoglobin within 30 ± 15 minutes before and at 60 ± 15 minutes after IMP initiation
- Measure INR within 30 ± 15 minutes before and at 60 ± 15 minutes after IMP initiation and document results
- Administer second dose of IMP, if needed
- Collect all transfusions and haemostatic therapies
- Collect chest tube drainage at 1, 6, 12 and 24 hours after chest closure
- Measure haemoglobin at 24 hours ± 1 hour after IMP initiation and document results
- Collect extubation time
- Collect concomitant medications
- Collect AEs and SAEs

6.1.4 Visit 3 (POD 2-7): Days 2-7 after IMP initiation (or at discharge, if earlier)

- Collect daily laboratory assessments where available as part of routine care
 - Chemistry (sodium, potassium, chloride, bicarbonate, pH)

- Haematology (complete blood count)
- Coagulation profile (e.g. PT, aPTT, INR, plasma fibrinogen level, ROTEM EXTEM CT and MCF, ROTEM FIBTEM MCF platelet count, platelet function)
- Safety labs (creatinine, liver function tests [ALT, ALP], bilirubin, troponin)
- Collect all transfusions and haemostatic therapies
- Record incidence of intracerebral haemorrhage, gastrointestinal haemorrhage and surgical re-exploration.
- Collect extubation time (if applicable)
- Collect length of stay in the ICU and hospital (if applicable)
- Collect concomitant medications
- Collect AEs and SAEs

6.1.5 Visit 4 (POD 30): Day 30 after IMP initiation (in person if in hospital, or by phone)

- Collect concomitant medications
- Collect AEs and SAEs
- Collect extubation time (if applicable)
- Collect length of stay in the ICU (if applicable)
- Collect length of stay in the hospital (if hospital stay is extended) and hospital readmissions
- Document patient outcome and survival at 30 days (still in hospital; dead or alive)

After Visit 4 or on POD-30, the clinical study is considered completed for the patient. No further study-related assessments will be performed, unless safety concerns (e.g., ongoing AEs) require follow-up.

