7.3.6.2 Local Laboratory

Table 6 summarises all test parameters performed as part of standard of care, the results of which will be collected as available.

Table 6 Test Parameters and Laboratories

Test	Material needed	Responsible Laboratory
Coagulation profile		
Point-of-care INR	Fresh blood	Local
(PT, aPTT, INR, fibrinogen activity via Clauss assay)	Citrated blood	Local
*ROTEM EXTEM CT	Citrated blood	Local
*ROTEM EXTEM MCF	Citrated blood	Local
*ROTEM FIBTEM MCF	Citrated blood	Local
PlateletWorks		
Haematology – standard panel as per local lab	Citrated blood	Local
Clinical chemistry – standard panel as per local lab	Serum	Local
Safety laboratory analyses		
Troponin	Serum	Local
ALT/ALP	Serum	Local
Bilirubin	Serum	Local
Creatinine	Serum	Local

ALT, alanine aminotransferase; ALP, alkaline phosphatase; CT, clotting time; MCF, maximum clot firmness; PT, prothrombin time; aPTT, activated partial thromboplastin time; ROTEM, thromboelastometry

*ROTEM or TEG can be measured

The haemoglobin and INR measurements will be performed at preestablished time points (**Table 7**).

Table 7 Mandatory Test Parameters and Laboratories

Test	Material needed	Responsible laboratory
Coagulation profile		
Point-of-care INR	Fresh blood Citrated blood	Local Local
Haematology		
Haemoglobin	Citrated blood	Local

Blood Sampling

All blood sampling will be performed as per standard practice at the local institution.

The *actual* time of blood sampling will be recorded. If the draw time is not recorded for samples processed in the laboratory, the draw time will be estimated based on the received time in the laboratory minus 10 minutes. For ROTEM and PlateletWorks, if the exact draw time is not recorded, the time for start of testing will be used for draw time.

Citrated and Fresh Blood

Citrated and fresh blood as required by the local laboratory will be collected and processed in accordance with local requirements.

Serum

Serum will be obtained for the determination of clinical chemistry, haematology, and safety labs (ALT, ALP, creatinine, bilirubin, troponin), where a serum blood sample has been collected.

Recording of Clinically Significant Abnormal Laboratory Values as AEs/ADRs

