## 7.1. Conventions

### 7.1.1. Baseline definition

Baseline will be defined as the last value on or prior to the first IMP administration.

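### Laboratory shift tables in SAP 11.2 run to an unnamed scheduled time point, although creatinine, ALT/ALP, bilirubin and troponin are sampled only as routine care provides; a worst-value table by arm should be added

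*SAP*

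**What the plan says.** **SAP 11.2 (Laboratory variables).** Quantitative results are summarised as "actual values at each scheduled time point and changes from baseline to each scheduled time point". Graphs are planned as well, and the SAP describes them thus: "mean concentration vs. time profiles (including standard deviations) will be plotted by treatment to illustrate any time trends". Shift tables show changes with respect to the laboratories' "reference ranges between baseline and a defined scheduled time point". Protocol 9.2.3.2 words its shift tables almost identically. Neither document says which time point is meant. SAP 7.1.1 does fix the starting point: "Baseline will be defined as the last value on or prior to the first IMP administration".

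**Protocol, sampling.**
- Section 6.1.3 (Visit 2, 0 to 24 hours) takes the safety laboratory tests only if they are available.
- Section 6.1.4 (Visit 3, days 2 to 7, or discharge if earlier) says: "Collect daily laboratory assessments where available as part of routine care".
- Section 6.1.5 (Visit 4, day 30) lists no laboratory test.
- Section 7.3.6.2 describes the Table 6 tests as standard of care, "the results of which will be collected as available".
- Tables 2 and 7 set mandatory times for haemoglobin and INR only.

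**Other laboratory displays.** SAP 11.2 also reports "number of patients, number of missing values, mean, SD, median, quartiles, minimum, maximum" and lists all individual results. It adds: "Patient listings will be provided showing individual laboratory abnormalities". Protocol 9.2.3.2 further plans a count and frequency of patients with clinically significant values. SAP 11.2 does not carry this over, although SAP 14 states that the SAP analyses match the protocol.

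**The concern.** A shift table to one time point suits a trial in which everyone is sampled on that day. Here the safety tests depend on what the treating team orders, and collection ends at discharge. Three consequences follow.

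- An abnormal creatinine or troponin that appears and resolves on days other than the chosen one does not enter the shift table.
- Visit 3 is one window that can hold several daily values. SAP 10.3 says which of several results to use for endpoint S14, but SAP 11.2 has no such rule for the safety tests. Two programmers could build different tables from the same data.
- Missing data are in general not imputed (SAP 7.1.2). The mean plotted for a late day therefore describes patients still in hospital whose team ordered the test. Attending clinicians are not blinded (Protocol 5.6), so ordering and discharge could differ by arm.

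At stake is how readable the laboratory safety comparison is. As SAP 11.2 stands, no by-arm table counts the patients who ever had an abnormal value. Protocol 1.1 discusses acute kidney injury and thrombotic events as possible risks of PCC, while also citing studies that found rates similar to FP.

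**Working it through.** The documents state no figure on this point, so there is none to reproduce. The calculation below is an illustration; every input except the seven-day span is an assumption.

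**Inputs**
- Seven daily slots: Visit 2 covers the first 24 hours and Visit 3 covers days 2 to 7 (Protocol 6.1.3 and 6.1.4).
- Assumed: an abnormal episode lasts *d* consecutive days within the seven, and each possible start day is equally likely.
- Assumed: on any day the test is done with probability *q*, independently of other days.
- Discharge is ignored, so real capture would be lower.

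**One fixed day.** An episode covers *d* of the seven days. Averaged over which day is chosen, the share seen is *q* × *d*/7. With *q* = 1 and *d* = 3 this is 3/7 = 43%.

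**Worst value.** An episode is seen if at least one of its days is tested: 1 − (1 − *q*)^*d*. With *q* = 0.7 and *d* = 2 this is 1 − 0.3² = 91%.

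| Episode length (days) | One day, q = 1 | Worst, q = 1 | One day, q = 0.7 | Worst, q = 0.7 | One day, q = 0.4 | Worst, q = 0.4 |
|---|---|---|---|---|---|---|
| 1 | 14% | 100% | 10% | 70% | 6% | 40% |
| 2 | 29% | 100% | 20% | 91% | 11% | 64% |
| 3 | 43% | 100% | 30% | 97% | 17% | 78% |
| 4 | 57% | 100% | 40% | 99% | 23% | 87% |
| 5 | 71% | 100% | 50% | >99% | 29% | 92% |

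The one-day columns are averages, and the choice of day matters. With complete testing, a 3-day episode is caught with probability between 20% and 60% depending on the day, and a 5-day episode between 33% and 100%.

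**Late-day means.** Let a share *h* of patients still be in hospital on a given day, all tested, with mean change *a* from baseline. Assume the discharged have mean change 0. The plotted mean is *a*; the mean over all patients is *h* × *a*. With *a* = 30 units, the plot shows 30, while the all-patient mean is 0.3 × 30 = 9, 0.5 × 30 = 15 or 0.8 × 30 = 24 for *h* = 0.3, 0.5 or 0.8. The documents give neither *h* nor *a*. The example shows the mechanism, not its size in this trial.

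**The case against.** The strongest case against has four parts.

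**The protocol is not silent on timing.** Table 1 marks clinical chemistry and the safety tests at Visits 2 and 3, and Visit 3 collects results daily where available. This stands. What is missing is narrower: required sampling, a named day for the shift table, and a rule for several values in one window.

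**The loss is not established.** A reader might infer that most transient abnormalities go unseen. The documents do not support that. It holds only for short episodes or sparse testing, and only if there is a single table. With complete daily testing one day catches on average 57% of 4-day and 71% of 5-day episodes, and a table for every day would miss none. SAP 13 leaves the output list to a separate document, which may settle how many tables are made.

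**Other displays remain.** Listings, minimum and maximum, and counts of patients and missing values stay in SAP 11.2. Protocol 7.3.6.2 requires specified clinically significant abnormalities to be recorded as AEs or SAEs. SAP 11.1 tabulates TEAEs by arm and lists acute kidney injury, acute liver injury and myocardial infarction as special cases. This stands, and it limits the consequence. It does not replace a by-arm laboratory count, because a listing is not a comparison and AE entries depend on the investigator's judgement of significance.

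**A worst value depends on how often patients are tested.** This is correct. If one arm were tested on 70% of days and the other on 40%, worst-value capture of 2-day episodes would be 91% against 64%. The table must therefore come with tests per patient by arm, and should be added to the existing shift table, not simply put in its place.

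**Conclusion.** The point holds as a cheap improvement to descriptive safety displays. SAP 11.2 relies on scheduled time points that neither document fixes for creatinine, ALT/ALP, bilirubin and troponin, and it leaves the shift-table time point unnamed. A one-day shift table can miss abnormalities on other days. The average capture of 14% to 71% for episodes of 1 to 5 days rests on uniform onset, complete daily testing and no discharge, none of which comes from the documents. Late-day means describe a selected group, by an amount that cannot be computed from the documents.

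A reader might go further and infer that kidney and cardiac safety rests on these tables, or that the laboratory comparison is biased in a known direction. Neither follows: AE reporting runs independently of the shift tables, and nothing in the documents shows that sampling or discharge will differ between arms. Haemoglobin and INR at their set times are outside the point, and the primary analysis is untouched.

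**What to change.** In SAP 11.2:

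1. Add, by arm, a shift table for the safety laboratory tests from baseline category to the worst category after IMP initiation, up to POD 7 or discharge. State which direction counts as worst for each test.
2. Show tests per patient by arm beside that table, because worst values rise with sampling frequency.
3. Under each day of the time profiles, show by arm the number still in hospital next to the number tested, so that discharged can be told apart from not tested.
4. If the single-time-point shift table is kept, name its time point or points and say which value is used when a window holds several.
5. Restore the count and frequency of patients with clinically significant values planned in Protocol 9.2.3.2, or record the omission in SAP 14.

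The cost is SAP wording, one derived variable per parameter and a few table shells. No new laboratory data are needed: investigators already classify clinical significance, and hospital length of stay is already collected. The remaining drawback is the dependence on sampling frequency, which item 2 makes visible but does not remove.

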## **12. Data Derivations and Data Transfer**

The results of all data transformations and derivations will be stored in analysis data sets.

Laboratory data received electronically will be integrated into the database.

## **13. Tables, Figures and Lists**

A complete List of Tables, Listings, Figures (TLFs) will be given in a separate document which can be updated without updating the SAP. The List will serve as a reference for the Sponsor, the Trial Statistician and the statistical programmer and describes the entire set of statistical output to be produced. Therefore, this List will be versioned and approved by both Ergomed and the Sponsor before commencing the statistical programming.

Each output page will have an appropriate heading specifying the study ID and abbreviated study title.

Each output page will show a common date and page numbers in the form 'Page [x / y]' where x denotes the current page within an output and y the total number of pages of that output. The output pages will not contain any other sequential page numbering.

All statistical output will identify the underlying analysis set(s) and indicate the number of patients/events in this set (N) and the number of patients/events actually contributing to the particular output (n).

All patient listings will contain, in addition to the patient ID, the treatment arm and the analysis set.

## 14. Changes from Analyses Specified in the Protocol

The described statistical analyses match those pre-specified in the study protocol.

## 15. Quality Control

The SAP was reviewed by the Trial Statistician before signature. In particular, the Trial Statistician has checked the consistency of the described methods and outputs with the actual version of the study protocol. In addition, a Sponsor representative has reviewed the SAP before final approval.

Log files of all SAS® programs used in the analysis will be checked for errors, warnings and suspicious notes by the statistical programmer. All findings will be either eliminated or commented upon. The final version of each program will be stored along with its log file in the electronic archive.

All programs will be validated by the program author or an independent statistical programmer, depending on the requested validation level selected in the List of TLFs.

The agreement of the program outputs with the SAP and their consistency and plausibility will be checked by the Trial Statistician. Moreover, the Trial Statistician will review the outputs regarding completeness, readability and comprehensibility.

The described process is associated with the 'normal' level of program validation. Additional levels of quality control can be specified in the List of TLFs (**Section 14**) for individual outputs.

## Appendix 1. Transformations/Derivations

Formulas for derived variables:

Variable	Definition / Derivation
Response (24h) (Treatment response)	= 'Effective' ('Yes') if no additional haemostatic intervention, such as administration of any systemic haemostatic agents (including platelets, cryoprecipitate, fibrinogen concentrate, activated recombinant factor VII, other coagulation factor products or a second dose of IMP) or any haemostatic interventions (including surgical re-opening for bleeding) is required from 60 minutes to 24 hours after initiation of the first dose of IMP. = 'Ineffective' ('No') otherwise.
Response (24h) (Global response)	= 'Positive' ('Yes') if no additional haemostatic intervention (as per the primary endpoint) is required and haemoglobin levels decrease by <30% (after accounting for red cell transfusions) from 60 minutes to 24 hours after initiation of the first dose of IMP. = 'Negative' ('No') otherwise.
ABC(time frame)	= Mean number of total Allogenic Blood Components (RBCs, Platelets and all [IMP and non-IMP] FP) transfused in specified time frame.
Non-IMP ABC(time frame)	= Mean number of total non-IMP Allogenic Blood Components (RBCs, Platelets, Cryoprecipitate and non-IMP FP) transfused in specified time frame.
Individual ABC(time frame)	= Mean number of individual Allogenic Blood Components (RBCs, Platelets, Cryoprecipitate and non-IMP FP) transfused in specified time frame.
Incidence of ABC(time frame)	= Incidence of transfusion of individual Allogenic Blood Components (RBCs, Platelets, Cryoprecipitate and non-IMP FP) in specified time frame.

### Transformations to be applied

In order that the sum of Allogenic Blood Products and its constituents adequately represent the exposure to donors, the following transformations will be applied before any derivations:

Platelets	
1 apheresis unit	= 4 allogeneic units,
1 non-apheresis unit	= 4 allogeneic units
Frozen plasma (used in transfusions):	
1 apheresis unit	= 1 allogeneic unit,
1 non-apheresis unit	= 1 allogeneic unit

Transfusion units without any information about apheresis are handled as apheresis units.
